6.1.1 COVE-based COVID-19 endpoint definition

The COVE-based primary COVID-19 endpoint is defined as the first occurrence of adjudicated symptom-triggered NAAT-confirmed COVID-19 based on the following criteria (same as in the Moderna mRNA-1273 COVE trial):

- At least TWO of the following systemic symptoms: Fever $\geq 38^{\circ}\text{C}$), chills, myalgia, headache, sore throat, new loss of taste or smell, OR
- At least ONE of the following respiratory signs/symptoms: cough, shortness of breath or difficulty breathing, OR clinical or radiographical evidence of pneumonia; AND
- At least ONE (post-baseline) nasal swab (or respiratory sample, if hospitalized) positive for SARS-CoV-2 by NAAT.

The date of a documented/adjudicated COVID-19 endpoint is the **later** date of a qualifying symptom and the date of the first confirmatory positive NAAT. This (event) date is supplied by the Endpoint Adjudication Committee.

6.1.2 CDC-based COVID-19 endpoint definition

The CDC-based definition of the COVID-19 endpoint is defined as symptomatic NAAT-confirmed COVID-19 based on CDC criteria, where the nucleic acid test NAAT may or may not be triggered by symptoms. The CDC-based COVID-19 endpoint is defined as the first occurrence of symptomatic NAAT-confirmed COVID-19 based on the following criteria:

- At least ONE of the following systemic or respiratory symptoms: Fever ($\geq 38^{\circ}\text{C}$), chills, cough, shortness of breath and/or difficulty breathing, fatigue, muscle and/or body aches [not related to exercise], headache, new loss of taste/smell, sore throat, congestion, runny nose, nausea, vomiting, or diarrhea; AND
- At least ONE (post-baseline) nasal swab (or respiratory sample, if hospitalized) positive for SARS-CoV-2 by NAAT.
- The symptom date and NAAT positive date must be within 14 days of each other. Specifically, if the onset of qualifying symptom(s) occurred prior to the specimen collection date of a NAAT-positive result, then the date of last reported symptom(s) must be after 14 days prior to the NAAT-positive date. If the onset of qualifying symptoms occurred after a NAAT-positive date, then the onset date of qualifying symptom(s) must be within 14 days of the NAAT-positive date.

The date of a COVID-19 endpoint according to the CDC-based definition is the **earlier** date of a qualifying symptom and the date of the first confirmatory positive NAAT that satisfy the criteria stated above.

For the Part B or the Part A+B analyses, although additional NAAT testing was performed at the M1 vaccination visit for study groups 1 & 3, not for study group 2 or 4, the randomization

between the bivalent and monovalent Month 6 boost arms was preserved within each study group. Therefore, the primary analyses in the RM6 cohort comparing between the randomized bivalent and monovalent boost arms will use the CDC1 endpoint that include NAAT testing results at Month 1. The CDC2 endpoints derived to exclude NAAT testing results at Month 1 for comparisons of COVID risk between different groups will only be applicable to the exploratory analyses that include also participants who missed the Month 6 vaccination, or received the monovalent boost outside of the randomization scheme.

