3. POST-MONTH 6 STAGE : to assess the relative risk of symptomatic COVID-19 after the Month 6 dose among those who received mRNA-1273 at Month 6 vs. those who received mRNA-1273.222 at Month 6, counting endpoints at least 14 days after the Month 6 dose until end of follow up.	3. COVID-19: same as above
4. POST-MONTH 6 STAGE : to assess the relative risk of severe COVID-19 after the Month 6 dose among those who received mRNA-1273 at Month 6 vs. those who received mRNA-1273.222 at Month 6, counting endpoints at least 14 days after the Month 6 dose until end of follow up.	4. Severe COVID-19: same as above

Primary Objectives	Primary Endpoints
5. To assess the safety and tolerability of mRNA-1273 and mRNA-1273.222 in adults who are at risk of severe COVID-19 in both the pre-Month 6 and post-Month 6 stages.	5. Adverse events: Solicited and unsolicited AEs collected for a subset of study participants. Serious adverse events (SAEs), adverse events of special interest (AESIs), collected for all participants throughout the study

 HIV-infection status and SARS-CoV-2 status are confirmed for each participant based on testing of samples collected during screening (serology) and at enrollment (NAAT). SARS-CoV-2 negative indicates both NAAT negative and serology negative.

 To be considered as a case of COVID-19 using the COVE case definition for the evaluation of the Primary Efficacy Endpoint, the following criteria must be met:

1. The participant must have experienced at least TWO of the following systemic symptoms: Fever ( $\geq 38^{\circ}\text{C}$ ), chills, myalgia, headache, sore throat, new loss of taste or smell, OR
2. The participant must have experienced at least ONE of the following respiratory signs/symptoms: cough, shortness of breath or difficulty breathing, OR clinical or radiographical evidence of pneumonia; AND
3. The participant must have at least 1 nasal swab (or respiratory sample, if hospitalized) positive for SARS-CoV-2 by NAAT within 14 days following the above systemic or respiratory symptoms.

 To be considered as a case of COVID-19 using the CDC-derived case definition for the evaluation of the Primary Efficacy Endpoint, the following criteria must be met:

1. The participant must have experienced at least ONE of the following systemic symptoms: Fever ( $\geq 38^{\circ}\text{C}$ ), chills, myalgia, headache, sore throat, new loss of taste or smell, OR

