2. The participant must have experienced at least ONE of the following respiratory signs/symptoms: cough, shortness of breath or difficulty breathing, OR clinical or radiographical evidence of pneumonia; AND
3. The participant must have at least 1 nasal swab (or respiratory sample, if hospitalized) positive for SARS-CoV-2 by NAAT within 14 days of any of the above systemic or respiratory symptoms.

 To be considered as a case of severe COVID-19 for the evaluation of the Secondary Efficacy Endpoint, the following criteria must be met:

- A confirmed case of COVID-19, per a Primary Efficacy Endpoint case definition, plus any of the following:
  - Clinical signs indicative of severe systemic illness, Respiratory Rate  $\geq 30$  per minute, Heart Rate  $\geq 125$  beats per minute, SpO2  $\leq 93\%$  on room air at sea level or PaO2/FIO2  $< 300$  mm Hg, OR
  - Respiratory failure or Acute Respiratory Distress Syndrome (ARDS), (defined as needing high-flow oxygen, noninvasive or mechanical ventilation, or ECMO), evidence of shock (systolic blood pressure  $< 90$  mmHg, diastolic BP  $< 60$  mmHg or requiring vasopressors), OR
  - Significant acute renal, hepatic, or neurologic dysfunction, OR
  - Admission to an intensive care unit or death.

Secondary Objectives	Secondary Endpoints
1. PRE-MONTH 6 STAGE: to assess the relative risk of symptomatic COVID-19 and of severe COVID-19 in Group 1 (PLWH who are SARS-CoV-2 negative at baseline) vs. in Group 2 (PLWH who are SARS-CoV-2 positive at baseline), counting endpoints at least 14 days after the last pre-Month 6 dose (i.e., dose 2 for Group 1 and dose 1 for Group 2) until the Month 6 dose.	COVID-19 and severe COVID-19 as defined for the primary endpoints
2. PRE-MONTH 6 STAGE: to assess the relative risk of symptomatic COVID-19 and of severe COVID-19 in Groups 1 and 3 together (participants who are SARS-CoV-2 negative at baseline regardless of HIV status) vs. in Groups 2 and 4 together (participants who are SARS-CoV-	COVID-19 and severe COVID-19 as defined for the primary endpoints

Secondary Objectives	Secondary Endpoints
2 positive at baseline regardless of HIV status), counting endpoints starting 1 day after dose 1, and counting endpoints at least 14 days after the last pre-Month 6 dose (ie,, dose 2 for Group 1 and dose 1 for Group 2) until the Month 6 dose.	

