6.1 Co-Primary COVID-19 endpoint

According to Version 8 of the protocol, all symptomatic COVID-19 endpoints will be evaluated using two case definitions, one used in the COVE study and the other using a case definition based on criteria from the CDC, with the latter being the leading definition given the lighter-symptom

nature of omicron infections observed and anticipated from the study. No multiplicity adjustments are applied to adjust for analyses of multiple COVID-19 endpoints.

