6.2 Severe COVID-19 endpoint

The severe COVID-19 endpoint is defined as the first occurrence of a COVE-based COVID-19 having at least one sign, symptom, or other evidence of severe disease (e.g., respiratory failure, shock, intensive care unit admission). The date of a documented/adjudicated severe COVID-19 endpoint is the later date of a symptom and the date of positive NAAT. This (event) date is supplied by the Endpoint Adjudication Committee.

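### The SAP's leading CDC-based endpoint uses a wider symptom list than the protocol's, and its severe endpoint leaves out CDC-based cases; the effect on the estimate is unknown in size and direction

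*SAP*

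**What the plan says.** **CDC-based COVID-19, protocol.** Section 3, footnote 3, sets the case criteria. For systemic symptoms: "The participant must have experienced at least ONE of the following systemic symptoms: Fever", followed by "chills, myalgia, headache, sore throat, new loss of taste or smell, OR". For respiratory signs: "cough, shortness of breath or difficulty breathing, OR clinical or radiographical evidence of pneumonia; AND". The swab must be "positive for SARS-CoV-2 by NAAT within 14 days of any of the above systemic or respiratory symptoms".

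**CDC-based COVID-19, SAP.** Section 6.1.2 gives a single list that needs one symptom. Its first part includes fatigue. It ends: "headache, new loss of taste/smell, sore throat, congestion, runny nose, nausea, vomiting, or diarrhea; AND". Evidence of pneumonia is not on it. Section 6.1 refers to Version 8 of the protocol for the two case definitions and ranks the CDC-based one first: "with the latter being the leading definition".

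**Severe COVID-19, protocol.** Footnote 4 requires: "A confirmed case of COVID-19, per a Primary Efficacy Endpoint case definition, plus any of the following". Footnotes 2 (COVE) and 3 (CDC) each describe themselves as a case definition for that endpoint. Section 6.4.3 gives CDC-based severe cases their own date rule, the earlier of the qualifying severe symptom and the positive swab.

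**Severe COVID-19, SAP.** Section 6.2: "The severe COVID-19 endpoint is defined as the first occurrence of a COVE-based COVID-19 having at least one sign". The date is the later of symptom and positive NAAT, supplied by the adjudication committee.

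**Threshold.** Protocol 6.4.3 and SAP 7.1 both make severe COVID-19 co-primary only with at least seven events.

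**The concern.** The two documents attach different meanings to the same endpoint name, and the endpoint affected is the one the SAP puts first. Protocol Section 2.1 only says that the COVE and CDC endpoint sets are calculated in parallel. The SAP does not mention that its list differs from footnote 3 and gives no reason for it. A reader of the results could not tell which definition had been prespecified for the lead comparison.

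The choice could matter in this trial. Participants are swabbed monthly after Month 6, and the protocol reports that 86% of pre-Month 6 infections were asymptomatic. The symptom list therefore decides which swab-detected infections become primary cases.

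For severe disease, the SAP's restriction could remove events from a count that decides whether protocol primary objective 4 is analysed as co-primary.

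**Working it through.** **1. Symptom lists compared item by item.**

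| Item | Protocol footnote 3 | SAP 6.1.2 |
|---|---|---|
| Fever, chills, myalgia, headache, sore throat, loss of taste or smell | yes | yes |
| Cough, shortness of breath or difficulty breathing | yes | yes |
| Clinical or radiographic pneumonia | yes | no |
| Fatigue, congestion, runny nose, nausea, vomiting, diarrhea | no | yes |

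Six items are added and one is omitted. Both documents use a 14-day link between symptom and swab for this definition.

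**2. Where the wider list appears in the protocol.** The SAP list is the same, item for item, as the surveillance list in protocol 9.5. That list decides when a symptom visit and swab are arranged. Section 9.5 refers to Primary Endpoint 1 for the case criteria, and Primary Endpoint 1 points to footnotes 2 and 3. Section 9.5 also requires 48 hours' duration for symptoms other than fever and respiratory ones (its list exempts loss of taste or smell too). SAP 6.1.2 has no duration rule.

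**3. COVE definition.** The symptoms in SAP 6.1.1 match footnote 2. The 14-day symptom-to-swab window in footnote 2 is not repeated there.

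**4. The plan's own power figure.** For the post-Month 6 stage, Table 6-2 gives 78% power at relative risk 2.0 with 76 events. A two-sided equal-tail exact binomial test, conditional on total events, with null proportion 0.5, alternative 2/(1+2) and alpha 0.05, gives 78.1%. The other five post-Month 6 rows also reproduce. No power figure is in dispute. Table 6-2 does not say which case definition its incidence refers to.

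**5. Illustration of the possible effect.** The inputs marked (a) are assumptions found in neither document.

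- Participants: 4,000 (protocol 6.3.1).
- Becoming NAAT positive after Month 6: 10% to 20% (a).
- Otherwise asymptomatic: 86% (protocol 2.1, a pre-Month 6 figure carried forward).
- Chance of an added symptom within the window: 5% to 10% (a).

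Extra cases x:

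- low: 4,000 × 0.10 × 0.86 × 0.05 = 17.2
- high: 4,000 × 0.20 × 0.86 × 0.10 = 68.8

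With 76 footnote 3 cases at a true ratio of 2.0, the arms hold 50.67 and 25.33.

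*If the extra cases are coincidental (ratio 1)*, the observed ratio is (50.67 + x/2)/(25.33 + x/2):

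- low: 59.27/33.93 = 1.75
- high: 85.07/59.73 = 1.42

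Exact-binomial power goes from 78% to about 72% (93 events) and 55% (145 events).

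*If the extra cases share the ratio of 2.0*, the ratio is unchanged and power rises to about 89% (93 events) and 98% (145 events).

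Starting from the 106-event row instead, the coincidental case gives (70.67 + 8.6)/(35.33 + 8.6) = 1.80 and (70.67 + 34.4)/(35.33 + 34.4) = 1.51.

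**6. Severe events.** The documents give no count of severe cases that would qualify under the CDC definition only, so the number lost under SAP 6.2 cannot be calculated.

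**The case against.** Several points on the other side are sound.

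- **The protocol is not entirely clean.** Section 9.5 calls the wider list prespecified and says it helps establish whether the endpoint criteria are met. A wider list also fits the stated aim of capturing mild cases. This may explain where the SAP list came from. It does not settle the matter, because 9.5 defers to Primary Endpoint 1 and its footnotes.
- **The mechanism is not peculiar to the added symptoms.** Under footnote 3, a lone headache or sore throat already makes a case.
- **Dilution is not shown.** A reader might infer that the wider list biases the lead ratio toward 1. The documents do not support that: every added case is still a NAAT-confirmed infection, and if the vaccines differ in preventing infection these cases carry signal. The 86% comes from a period when the study had used only the COVE approach, so the pool in step 5 may be too large.
- **A loss of severe events is not shown.** A CDC-only severe case would mostly need a severity criterion without cough, breathing difficulty or pneumonia and with fewer than two systemic symptoms, or a swab that preceded symptoms. There may be almost none.
- **Omitting pneumonia matters little**, since cough or breathing difficulty alone qualifies.
- **The missing COVE window is probably an unrepeated criterion.** SAP 6.1.1 specifies adjudicated, symptom-triggered cases as in the COVE trial, and the committee applies the COVE criteria.
- **A rationale may exist elsewhere.** SAP Section 6 says its definitions come from the pre-Month 6 SAP, which is not among the documents. If Part A used the wider list, reverting in Part B alone would weaken comparability.

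These points limit the consequence. They do not remove the conflict between the two current documents.

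**Conclusion.** The mismatch is established by the text alone and needs no assumption. The SAP's leading endpoint has six symptoms that footnote 3 lacks and lacks one that it has. The SAP's severe endpoint excludes a class of cases that footnote 4 admits and protocol 6.4.3 dates. Followed as written, the SAP would produce a lead result, and a severe count against the threshold of seven, on endpoints the protocol does not define.

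It would be too strong to say that all the SAP's co-primary endpoints depart from the protocol: the COVE symptom list matches, and COVE-based COVID-19 is analysed alongside the CDC-based endpoint.

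The effect on the estimate is unknown in size and direction. The range of 1.75 to 1.42 for a true 2.0 holds only if the added cases are coincidental, on the assumed inputs in step 5 and with 76 protocol-defined events. If those cases share the true ratio, power rises instead. The effect on the severe count is unquantified and may be close to zero.

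**What to change.** Settle the following before unblinded data are analysed.

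1. **One primary symptom list in both documents.** Either use the footnote 3 list in SAP 6.1.2, or amend footnote 3 to the wider list. The second route keeps comparability if Part A used the same list. Whichever is chosen, report the other as a prespecified sensitivity analysis and state the reason for the choice.
2. **Severe COVID-19.** Define it in SAP 6.2 as the footnote 4 criteria in a case meeting either definition. Use the protocol 6.4.3 date rule for CDC-based cases. Report COVE-only severe cases as a sensitivity analysis, and say that the seven-event threshold applies to the either-definition count.
3. **COVE window.** Repeat the 14-day symptom-to-swab window from footnote 2 in SAP 6.1.1 as a clarification.

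The cost is SAP wording (or a protocol amendment) and one extra endpoint derivation; the symptoms on both lists are already collected. If footnote 3 is chosen, there may be fewer CDC-based cases and less comparability with Part A.

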#### 6.4.3 Analysis of relative risk between treatment arms

For the assessment of the coprimary efficacy objectives, this study uses two approaches for determining symptomatic COVID-19 cases, as previously defined in Section 3. For survival data analyses, the time of all participant-level failure and censoring events are reported relative to the time of enrollment (ie, first vaccination) for the pre-Month 6 stage objectives, and relative to the time of Month 6 dose for post-Month 6 stage. For the COVE-based endpoint definition, the time of diagnosis of COVID-19 and severe COVID-19 will be determined by the EAC adjudicators. For the CDC criteria-based definition, the time of diagnosis of lab-confirmed clinical COVID-19 is defined as the minimum date of reported qualifying COVID-19 symptoms and collection date of SARS-CoV-2 positive result (both must occur), and the time of diagnosis of severe COVID-19 to be the minimum date of reported qualifying severe COVID-19 symptoms and collection date of SARS-CoV-2 positive result (both must occur).

The time of diagnosis of the SARS-CoV-2 infection endpoint is the draw time of the first sample with a positive test result by either antibody seroconversion assays or by virus-detection via NAAT. The serology assays are used to ascertain infections occurred anytime during the study among baseline SARS-CoV-2 negative (NAAT and serology negative) participants to address Secondary objectives 1-8. The NAAT are used to ascertain recent or ongoing infections among both baseline SARS-CoV-2 negative and positive participants to address exploratory objectives. The time of diagnosis of the asymptomatic endpoint is the draw time of the first sample with a positive test result by virus detection assays or seroconversion with no reported COVID-19-like illness episodes between enrollment and 14 days after the timepoint at which SARS-CoV-2 infection is ascertained. In case of reinfection of SARS-CoV-2, the first occurrence of a given endpoint is considered.

In the primary and most secondary efficacy analyses, the failure times of participants never observed to be diagnosed with a given clinical endpoint will be right censored at the date of last contact at which endpoint status was assessed or study termination. Participants who report outside COVID-19 vaccines will be censored at the time of receiving such vaccination. Except where otherwise

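### SAP 6.1.2 can date a CDC-based event more than 14 days before the positive swab, because its pre-swab rule limits the last reported symptom and not the onset

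*SAP*

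**What the plan says.** SAP 6.1 names the COVE and CDC case definitions, "with the latter being the leading definition given the lighter-symptom" nature of Omicron infections. So the CDC-based definition carries the main COVID-19 result.

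The timing bullet in SAP 6.1.2 has three parts:

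- A general link: "The symptom date and NAAT positive date must be within 14 days of each other".
- Onset before the swab: "then the date of last reported symptom(s) must be after 14 days prior to the NAAT-positive date".
- Onset after the swab: "then the onset date of qualifying symptom(s) must be within 14 days of the NAAT-positive date".

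The event then takes the earlier "date of a qualifying symptom and the date of the first confirmatory positive NAAT that satisfy the criteria stated above". Protocol 6.4.3 says that the CDC-based time of diagnosis "is defined as the minimum date of reported qualifying COVID-19 symptoms and collection date of SARS-CoV-2 positive result (both must occur"). Protocol Section 3, footnote 3, sets the case criterion as a sample "positive for SARS-CoV-2 by NAAT within 14 days of any of the above systemic or respiratory symptoms". In the SAP's CDC symptom list only loss of taste or smell has to be new.

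The COVE-based definition works differently. SAP 6.1.1 uses the later of the two dates, and "This (event) date is supplied by the Endpoint Adjudication Committee". Protocol 2.1 notes that the CDC criteria do not require adjudication.

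**The concern.** The two halves of the bullet are not symmetric. Onset after the swab must fall within 14 days of it. Onset before the swab may lie at any distance, provided the symptom was still being reported less than 14 days before the swab. Because the earlier date is used, a persistent cough or headache can set the event date well before any evidence of infection.

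Two things are at stake for the leading endpoint:

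- **Window.** The primary analysis counts from 14 days after the Month 6 dose (SAP 7.1). An infection first detected inside the window can be dated outside it.
- **Risk set.** The Cox model runs on calendar time because the epidemic changes unpredictably (SAP 10.3). An event dated weeks too early is compared with the wrong set of participants at risk, at the wrong point in the epidemic.

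No adjudicator sees CDC-based dates, so an implausible one would not be caught by that route. Routine swabs are monthly after Month 6 regardless of symptoms (Protocol 2.1.1), so a positive swab can coincide with a symptom that has another cause.

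**Working it through.** **Step 1. The clauses side by side.**

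| Clause | Date that is limited | Limit |
|---|---|---|
| Opening sentence, SAP 6.1.2 | an unspecified symptom date | 14 days either side |
| Onset before swab, SAP 6.1.2 | last reported symptom | less than 14 days before swab |
| Onset after swab, SAP 6.1.2 | onset | 14 days after swab |
| Dating sentence, SAP 6.1.2 | an unspecified symptom date, subject to the criteria | none of its own |
| Dating rule, Protocol 6.4.3 | earliest reported qualifying symptom | none |

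The second and fifth rows together allow an event date that the first row rules out.

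**Step 2. Day arithmetic.** Day 0 is the Month 6 dose. Appendix K puts that dose at study day 169 and the Month 7 and Month 9 visits at days 197 and 265, so swabs at those visits fall on day 197 − 169 = 28 and day 265 − 169 = 96. Counting starts on day 14.

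- Qualifies if onset ≤ swab and last symptom > swab − 14, or if onset follows the swab by at most 14 days.
- As written: event date = min(onset, swab).
- Capped reading, in which the opening sentence governs: event date = max(onset, swab − 14) for onset before the swab.
- Proposed rule: onset if it is at most 14 days before the swab, otherwise the swab date.

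| Course (all qualify) | As written | Capped reading | Proposed rule |
|---|---|---|---|
| (a) Cough from day −60, still present, swab day 28 | −60, before window | 14, counted | 28, counted |
| (b) Same cough, swab day 96 | −60, before window | 82, counted | 96, counted |
| (c) Cough days 5–20, swab day 28 | 5, before window | 14, counted | 28, counted |
| (d) Cough from day 30, still present, swab day 96 | 30, counted but 66 days before swab | 82, counted | 96, counted |
| (e) New cough day 26, swab day 28 | 26, counted | 26, counted | 26, counted |
| (f) Cough days 10–22, swab day 22 | 10, before window | 10, before window | 10, before window |

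Cases (a) to (d) change with the reading. Case (e), the ordinary course, does not. Case (f) falls before the window under every rule, so a handling rule is needed in any event.

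**Step 3. Events dated before day 14.** Protocol 6.4.3 removes from the analysis a participant whose endpoint precedes the counting period. SAP Section 4 takes the first occurrence after the time origin, which leaves the participant at risk. Neither counts the back-dated event, and they give different denominators.

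**Step 4. Scale, under an assumption.** The documents give no frequency. For context, Table 6-2 (post-Month 6, annual incidence 2.5%, relative risk 2.0) states 76 events and 78% power. An exact two-sided binomial test at 0.05 with event probability 2/(1 + 2) gives 78.1%, and all six post-Month 6 rows reproduce. Suppose, purely as an assumption, that 5% to 20% of events were lost: 76 × 0.95 ≈ 72 and 76 × 0.80 ≈ 61 events remain. The Schoenfeld approximation, Φ(√D × ln 2 / 2 − 1.96), gives 85.6% at 76 events, 83.7% at 72 and 77.2% at 61. The exact test gives 78.1%, 81.0% and 72.5%. It is not monotone because the test is discrete.

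**The case against.** The strongest reply is that the text already contains the cap. The bullet opens with a 14-day link, and the dating sentence refers to dates that meet the stated criteria and speaks of a symptom, not its onset. On that reading cases (a) to (d) are all counted. This is a fair reading, and a reader who infers that the SAP has no 14-day limit at all goes too far. But the detailed clause that follows implements the link without capping onset, and the protocol's minimum-date rule points the same way. Two programmers could derive different dates for the leading endpoint.

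Trial procedures also narrow the scenario. Symptoms are elicited about every two weeks, and a cough of any duration prompts a swab within 72 hours (Protocol 9.5). Vaccination is delayed for a participant with COVID-19 symptoms, and a swab is taken at vaccination visits (Protocol 9.3). Cases (a) and (b) therefore need a symptom that was not treated as illness, and (c) and (d) a missed or negative symptom swab. This makes the problem less frequent but does not rule it out.

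A reader might also infer that chronic symptoms wrongly turn asymptomatic infections into cases, citing the 86% of pre-Month 6 infections that were asymptomatic or the association of tuberculosis history with CDC endpoints (SAP 7.1). The documents do not support that step. Protocol 2.1 chose a broad, one-symptom definition on purpose, and footnote 3 ties the swab to any listed symptom, not to its onset. Neither figure shows how often long-standing symptoms were recorded.

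Finally, checks exist. The COVE-based and severe endpoints use the later, adjudicated date, and Secondary analysis I counts from day 1, so it recovers events dated on days 1 to 13. It does not recover (a) or (b).

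**Conclusion.** The dating rule for the leading endpoint is internally inconsistent and should be corrected. As operationalized, it allows event dates more than 14 days before the positive swab: 88, 156, 23 and 66 days in cases (a) to (d). Three of those four infections, first detected inside the window, would be lost from the primary analysis.

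The size of the effect cannot be stated. Any percentage of affected events is an assumption, and the power range above is an illustration only.

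A reader might infer bias in favor of one vaccine. The documents do not support that: Month 6 assignment under Version 6 was randomized and participants were blinded to it (SAP Section 2), so misdating should fall on both arms alike. The expected cost is lost or misplaced events. This argument covers the randomized comparison only.

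The conclusion rests on reading the symptom date as onset, which Protocol 6.4.3 favors and the SAP does not settle. It concerns the CDC-based endpoint alone.

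**What to change.** 1. Leave the CDC case definition as it is. In SAP 6.1.2, define the symptom date used for dating as an onset date and require it to lie within 14 days of the positive NAAT. Where no qualifying symptom began within the 14 days before the swab, use the NAAT collection date.
2. State in SAP Section 4 how an event dated before the counting window is handled: participant excluded, as in Protocol 6.4.3, or kept at risk for a first later occurrence. Case (f) shows that the new dating rule does not remove this need.
3. SAP Section 6 says the pre-Month 6 definitions are reused. Apply the same dating rule there, or report it there as a sensitivity analysis, so that the two stages stay comparable.
4. Do not require onset within 14 days for case status in the main analysis. That would narrow a deliberately broad definition and drop true illnesses first swabbed late. It can serve as a sensitivity analysis.

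The cost is a sentence or two in the SAP, a small change in derivation code and probably a few re-dated events. If pre-Month 6 results are already reported, item 3 adds one rerun.
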